6.4 Role of the CDC Investigators in the Project

This study is funded by a CDC contract with Duke University and Kaiser Permanente as Task Orders in the CISA Project Contract. The Duke University PI ([name]) will oversee the study in partnership with the Kaiser Permanente PI ([name]). CDC staff will collaborate with both sites to develop the protocol, conduct the study, ensure the study is aligned with US Department of Health and Human Services public health priorities, and analyze the data and disseminate the results. CDC may receive access to coded data not containing any directly identifying information.

7 HUMAN SUBJECTS

7.1 Human Subjects Involvement, Characteristics, and Design

Duke and Kaiser investigators will be responsible for submitting the protocol, informed consent (**Appendix A**), memory aids (**Appendix B**), recruitment letters, flyers (**Appendix C**), and any written or verbally conveyed materials (**Appendix D**) specific to this project to their institutional review boards. CDC staff will be responsible for submitting materials to the CDC for review and obtain reliance on Duke IRB.

To facilitate subject recruitment at the practices, we will request a waiver of consent and HIPAA authorization for ascertainment (identification, selection) and/or recruitment of potential subjects while recording identifiable private health information (PHI) prior to obtaining the subject’s consent. This information will be obtained from review of the electronic scheduling and medical record systems in the clinics in order to determine eligibility for study enrollment. We will review information only the minimum amount of information necessary to determine potential eligibility, e.g. to consent will be used to recruit and screen only. Use of PHI in this manner involves no more than minimal risk to subjects and no information will leave the study sites.

Continuing reviews will be submitted to the IRBs on an annual basis. Protocol deviations or concerns about study integrity will be reported promptly to the overseeing IRB in accordance with institutional requirements.

7.2 Sources of Material

Medical history, immunization history and concomitant medication history will be obtained from the medical record and from patient report. Demographic information will be obtained from the medical record and patient report. Subjects will record solicited adverse reactogenicity events and any medical intervention sought on the day of and 7 additional days following Visit 1 and Visit 2 on the memory aid (**Appendix B**). Memory aid information will be reported to the study team during a telephone call or in the web-based REDCap system. The research staff will assess temperature. Medical records will be reviewed to assess for the occurrence of febrile seizures or serious adverse events during the entire study period.

7.3 Potential Risks and Benefits

PCV13, DTaP and IIV are FDA licensed vaccines approved for use in children 12-16 months of age. These vaccines are standard clinical practice and recommended by the CDC and ACIP. Participants will be provided with the CDC Vaccine Information Statements (VIS) for PCV13, DTaP and IIV (<http://www.cdc.gov/vaccines/hcp/vis/vis-statements/dtap.html>) and <http://www.cdc.gov/vaccines/hcp/vis/vis-statements/pcv13.html>).

IIV risks include minor problems such as soreness, redness, swelling, or pain where the shot was given, hoarseness, sore, red or itchy eyes, cough, fever, aches, headache, itching, fatigue, all of which usually occur within 1-2 days of vaccination and are self-limiting. Syncope (fainting) can occur in association with administration of injectable vaccines but is less likely in young children. More serious problems including a small increased risk of Guillain-Barré Syndrome estimated at 1 or 2 additional cases per million people vaccinated. This is much lower than the risk of severe complications from influenza infection, which can be prevented by IIV. In addition, any medication can cause a severe allergic reaction, or anaphylaxis, which is estimated at ~1 in a million doses of IIV (<http://www.cdc.gov/vaccines/hcp/vis/vis-statements/flu.html>).

DTaP risks include mild problems such as redness, swelling, and pain where the shot was given, redness or swelling where the shot was given, fever, chills, sore joints, headache, body aches, fatigue, nausea, vomiting, diarrhea, stomach ache, rash, and swollen glands, all of which usually occur within 1-2 days of vaccination and are self-limiting. Moderate problems include higher severity of mild problems and swelling of the entire arm or leg in which the injection was given. Rarely, local injection site symptoms limit the ability to perform usual activities and require medical attention.

PCV13 risks include mild problems such as drowsiness, temporary loss of appetite, redness, swelling, or tenderness where the shot was given, fever, increase in fussiness and irritability. Young children may be at increased risk for febrile seizure.

Problems that could happen after any injected vaccine:

- People sometimes faint after a medical procedure, including vaccination. Sitting or lying down for about 15 minutes can help prevent fainting, and injuries caused by a fall. Subjects should inform their doctor should they feel dizzy, or have vision changes or ringing in the ears. This is unlikely in small children.
- Any medication can cause a severe allergic reaction. Such reactions from a vaccine are very rare, estimated at about 1 in a million doses, and would happen within a few minutes to a few hours after the vaccination. As with any medicine, there is a very remote chance of a vaccine causing a serious injury or death.
- The Advisory Committee on Immunization Practices (ACIP) does not make specific recommendations about simultaneous or sequential administration of PCV13, DTaP and IIV for young children. However, based on the ACIP General Recommendations, PCV13, DTaP and IIV (all inactivated vaccines) may be administered to young children either simultaneously or sequentially. The current General Best Practice Guidelines for Immunization (assessed at <https://www.cdc.gov/vaccines/hcp/acip-recs/general-recs/index.html>)

Simultaneous administration of vaccines is defined as administering more than one vaccine on the same clinic day, at different anatomic sites, and not combined in the same syringe. Experimental evidence and extensive clinical experience provide the scientific basis for administering vaccines simultaneously. Simultaneously administering all vaccines for which a person is eligible at the time of a visit increases the probability that a child, adolescent, or adult will be vaccinated fully by the appropriate age.

Pneumococcal conjugate, Diphtheria toxoid, tetanus toxoid and acellular pertussis (DTaP), and quadrivalent inactivated influenza vaccine (IIV) can be administered simultaneously.

There is the potential risk of loss of confidentiality about information obtained as part of this study. There is a potential risk of a short delay in influenza protection by delaying the receipt of influenza vaccine 2 weeks. If parents are concerned that their child has an influenza-like illness (characterized by fever and irritability, cough, sore throat, or vomiting), they should seek care for their child with their child's health care provider. If their child's provider suspects or determines that their child has influenza, there are medications to treat influenza illness and their provider may opt to treat their child with one of these medications.

7.4 Adequacy of Protection Against Risks

7.4.1 Protections against Risk

Subjects will be counseled on possible side effects following vaccination and followed closely during the 8 days post-vaccination for assessment of moderate to severe systemic reactogenicity. Subjects with a prior history of any severe reaction following IIV, PCV13 or DTaP will be excluded from study enrollment.

Every effort possible will be made to keep information about participants confidential. Computerized participant information will be kept in password protected files on secured servers. Paper case report forms will be kept in locked files belonging to the study personnel. Any publications resulting from this work will not contain any identifiable participant information.

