 - Parent(s)/LAR(s) electing to use REDCap will only be called/contacted on Study Day 3 following Visit 1 if missing fever information or if out of range fever values and will only be called/contacted on Study Day 9 following Visit 1 if missing information
 - All parent(s)/LAR(s) electing to use the paper memory aid only will be called/contacted on Study Day 3 following Visit 1.
 - All children will return for a visit on Visit 2 on Day 15. Remind parents using paper memory aid only to return memory aid at Visit 2.

Visit 1A, Study Day 3 (window Days 3-6) Memory Aid Check - Phone Call/E-mail Follow-up

- *REDCap Follow-Up for Memory Aid Information*
 - Review of REDCap information submitted for fever only on Day 1 and Day 2 for completeness and out of range values for fever.
 - If missing fever information or out of range fever values, contact parent(s)/LAR(s) to review the memory aid data for Day 1 and Day 2 and obtain any missing fever information or clarify any out of range fever values.
 - Instruct parent to enter any missing days of data in REDCap

- Record missing information regarding fever on paper case report form (CRF)
- If missing days of information for solicited adverse events, medical care utilization, antipyretic use, occurrence of febrile seizure or occurrence of a serious event remind parent to complete information in REDCap,
- *Paper Memory Aid Completion*
 - Contact parent(s)/LAR(s) to review and obtain Day 1 and Day 2 memory aid information for fever only (completeness and out of range values)
 - Record information regarding fever on paper CRF
 - Remind parent(s)/LAR(S) to bring the paper memory aid to Visit 2
 - Confirm date of next scheduled clinic visit appointments.

Visit 1B, Study Day 9 (window Days 9-12) Memory Aid Check – Phone Call/E-mail Follow-up

- *REDCap Follow-Up for Memory Aid Information*
 - Review of electronically submitted memory aid information (fever, solicited adverse events, medical care utilization, antipyretic use, occurrence of febrile seizure, or occurrence of a serious adverse event) for Days 1-8 for completeness
 - If missing information, contact parent(s)/LAR(s) to review the memory aid data for Days 1-8 and obtain any missing information
 - Instruct parent to enter missing days of data into REDCap
 - Record missing information on a paper CRF
- *Paper Memory Aid Completion*
 - No scheduled follow-up for this visit

Visit 2, Study Day 15 (window Days 15 – 22) Clinic Visit

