5.6 Solicited Systemic Adverse Events (Days 1-8 Following Visits 1 and 2)

Temperature and other solicited systemic adverse events will be assessed and documented by parent(s)/LAR(s) after Visit 1 and Visit 2. Beginning on the evening of Visit 1 and Visit 2 (Day 1), parent(s)/LAR(s) will measure and record their child's temporal artery temperature using the study-supplied thermometer as described in more detail in Section 5.4.

Parent(s)/LAR(s) will rate solicited systemic adverse events (other than fever) according to grading in **Table 2** beginning on the evening of Study Visits 1 and 2 (Day 1) and for the next 7 days following the study visits (i.e. through Day 8). Each of the following symptoms fussiness or irritability, change in eating habits and sleepiness, should be assessed each day. For the day of vaccination, symptoms should be assessed from the time of vaccination until the time information is recorded. For each subsequent day through Day 8 symptoms should be assessed from the time information is recorded on the previous day until the time it is recorded on the subsequent day. Grading for the child solicited systemic symptoms will be recorded on the study-supplied paper memory aid.

Parent(s)/LAR(s) will be instructed to notify child's primary care provider promptly in addition to study staff using the 24-hour contact number provided in the memory aid in the event of any severe (Grade 3) temperature elevation or solicited systemic adverse event. Parent(s)/LAR(s) who at any time report severe solicited adverse events or express any concern about symptoms/unsolicited events to the study team will be encouraged to follow up with their child's primary care provider. Study staff will assist with coordination of referral appointments as necessary.

Table 2: Fever Assessment and Solicited Systemic Adverse Events				
	None	Mild (Grade 1)	Moderate (Grade 2)	Severe (Grade 3)
Temporal Artery Temperature °C °F	≤ 37.9 ≤ 100.3	≥ 38.0 - ≤ 38.5 ≥ 100.4 - ≤ 101.3	≥ 38.6 - ≤ 39.5 ≥ 101.4 - ≤ 103.1	≥ 39.6 ≥ 103.2
Fussiness or Irritability	None	Less playful than usual but not requiring more attention and able to console	Requiring increased attention but able to console	Unable to console
Change in eating habits	None	Eating less than normal for 1 to 2 feeds/meals	Missed 1 or 2 feeds/meals completely	Refuses ≥3 feeds/meals or refuses most feeds/meal

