Drowsiness or Sleepiness	None	Drowsiness but still interested in surroundings and did not miss feed or meal	Not interested in surroundings or did not wake up for a feed or meal	Sleeps most of the time or difficult to wake up

*Cut off values for fever referenced from *Fluzone Quadrivalent Package Insert* (https://www.vaccineshoppe.com/image.cfm?pi=fluQIV&image_type=product_pdf)

For this study, solicited adverse events will be documented using either the electronic memory aid through REDCap or the paper memory aid. The preferred method for documentation in this study is REDCap. All parent(s)/LAR(s) will be encouraged to use the paper memory aid as a tool to initially record solicited adverse events and then enter information into REDCap. However, they can directly enter solicited adverse event information into REDCap if desired without using paper. For parents electing to use REDCap, missing solicited adverse event data will be verified with the parent(s)/LARS on day 9 as needed following Visits 1 and 2. Parents/LAR using the paper memory aid alone will submit the Visit 1 memory aid to study staff during Visit 2, and will mail the study Visit 2 memory aid to the study team following the 8-day post-visit 2 period. The study team will review the paper memory aid at the time of receipt.

For parent(s)/LAR(s) entering data into REDCap, if there are data discrepancies for solicited adverse event entered directly into REDCap or obtained over the phone, the information provided by the parent in REDCap will be counted as the correct information unless verified as otherwise by study staff.

For parent(s)/LAR(s) using only the paper memory aid, if there are data discrepancies for solicited adverse events recorded on the memory aid, the information on the memory aid should be taken as the correct adverse event information unless verified as otherwise by study staff.

5.7 Medical Care Utilization, Antipyretic Use, and Febrile Seizures (Days 1-8 Following Visits 1 and 2)

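### Section 7.4.1 describes close follow-up for moderate to severe reactions over 8 days, but scheduled staff review inside those days covers only Day 1–2 fever

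*Combined protocol and SAP*

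**What the plan says.** Protocol section 7.4.1 lists, among the protections against risk, that children will be "followed closely during the 8 days post-vaccination for assessment of moderate to severe systemic reactogenicity". The reactions in scope are those graded in section 5.6, under "Table 2: Fever Assessment and Solicited Systemic Adverse Events": temperature, fussiness, eating and drowsiness. In that table, moderate means Grade 2 and severe means Grade 3.

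Section 5.1 sets out what staff look at and when.

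- **"Visit 1A, Study Day 3 (window Days 3-6) Memory Aid Check"**. For REDCap families the task is "Review of REDCap information submitted for fever only on Day 1 and Day 2 for completeness and out of range values for fever". Paper families are all contacted, for the same two days of fever data. For REDCap families, other items prompt only a reminder to complete the entry (the bullet opens "If missing days of information for solicited adverse events, medical care utilization, antipyretic use"). Visit 2A repeats this after Visit 2.
- **Visit 1B (Days 9–12) and Visit 2B (Days 9–15 after Visit 2)**. Staff check all REDCap items for Days 1–8 for completeness. Paper families have no scheduled contact here, beyond a possible reminder if the second diary is not returned.
- **Visit 2 (Days 15–22)**. Staff collect and review the first paper diary. The second is posted after Day 8 and read on receipt.

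Section 5.6 agrees for REDCap families: "missing solicited adverse event data will be verified with the parent(s)/LARS on day 9 as needed". It also gives parents a 24-hour number and asks them to notify the primary care provider and study staff promptly "in the event of any severe (Grade 3) temperature elevation or solicited systemic adverse event". Parents who report severe events or voice a concern are encouraged to see their provider, with staff help on referral.

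**The concern.** Section 7.4.1 describes something the study does over a defined period, for reactions of moderate grade and above. Section 5.1 has staff read one graded item, on two of the eight days, and for data quality. Section 5.6 fills part of the gap through the parent, at Grade 3 only. The three sections therefore describe different levels of oversight.

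The practical consequence is narrow. If a parent enters a Grade 3 reaction in REDCap and does not telephone, the entry can stay unread in the study's own database until after Day 8. The later check would not necessarily lead to a call either. Section 5.1 has REDCap parents contacted on Day 9 only if information is missing, so a complete diary triggers no scheduled contact before Visit 2. At Visit 1A the trigger is missing or out-of-range fever data. The protocol does not define out of range, so it is unclear whether a plausible Grade 3 temperature would prompt contact.

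The sentence stands in the section on adequacy of protection, in a study of children aged 12–16 months without a designated monitoring board (section 5.8). Anyone relying on it should be able to see what is actually done.

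**Working it through.** The plan gives no figure for these lags, so there is none to reproduce. The check sets each scheduled review window from section 5.1 against Days 1–8.

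**Step 1: which reviews fall inside Days 1–8.**

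| Review | Window | Inside Days 1–8? | Content |
|---|---|---|---|
| Visit 1A / 2A | Days 3–6 | Yes | Fever on Days 1–2 |
| Visit 1B (REDCap) | Days 9–12 | No | All items, completeness |
| Visit 2 (paper) | Days 15–22 | No | All items |
| Visit 2B (REDCap) | Days 9–15 after Visit 2 | No | All items, completeness |
| Second diary (paper) | On receipt, after Day 8 | No | All items |

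Per visit, the scheduled staff reviews inside the 8 days number one for Day 1–2 fever, none for Day 3–8 fever, and none for the three non-fever items.

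**Step 2: lag from entry to first scheduled look after Visit 1.** Lag = review day − day of the entry. The shortest lag pairs the latest entry day with the earliest review day. The longest pairs the earliest entry day with the latest review day.

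| Item | Route | Shortest | Longest |
|---|---|---|---|
| Day 1–2 fever | Either | 3 − 2 = 1 day | 6 − 1 = 5 days |
| Day 3–8 fever | REDCap | 9 − 8 = 1 day | 12 − 3 = 9 days |
| Day 3–8 fever | Paper | 15 − 8 = 7 days | 22 − 3 = 19 days |
| Non-fever grades | REDCap | 9 − 8 = 1 day | 12 − 1 = 11 days |
| Non-fever grades | Paper | 15 − 8 = 7 days | 22 − 1 = 21 days |

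**Step 3: after Visit 2.** For REDCap non-fever grades the lag is 9 − 8 = 1 day to 15 − 1 = 14 days. For paper families no date is fixed. Day 1–2 fever is again 1–5 days. Section 7.4.1 speaks of the period after vaccination, so these lags bear on it only for the sequential group, which receives influenza vaccine at Visit 2.

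**Step 4: the grade named in each section.** Section 7.4.1 names moderate to severe, that is Grades 2 and 3. The notification instruction in section 5.6 names Grade 3. No section instructs a parent to contact staff at Grade 2, and no scheduled staff reading of Grade 2 non-fever entries falls inside the 8 days.

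**The case against.** The best reply is that section 7.4.1 is a summary. It promises follow-up for assessment, not staff reading of every grade as it is entered. Parents grade each symptom daily on a standard scale through Day 8. Severe events go promptly to both the child's own provider and the study. The diary prompts for serious adverse events and febrile seizures (section 5.8), and Table 1 of section 5.1 lists collection of both at Visits 1A and 2A. The fever that staff do review falls in the primary outcome window, and section 7.3 says the usual effects of the influenza and DTaP vaccines occur within 1–2 days. No endpoint or analysis is affected.

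Much of this stands, and it rules out several readings that a reader might infer.

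- **That staff review no graded reaction inside the 8 days.** Temperature is graded, and Day 1–2 fever is reviewed on Days 3–6 for both REDCap and paper families.
- **That the protection is not delivered.** The Grade 3 notification route operates inside the 8 days.
- **That Grade 2 reactions have no route to staff.** Sections 5.6 and 5.8 cover any parent who raises a concern. What is missing is an instruction to do so.
- **That lags of 11 or 21 days apply to every graded reaction.** Those maxima belong to the non-fever items.
- **That the minimal-risk classification rests on section 7.4.1.** Section 7.5.1 bases it on routine vaccination consistent with ACIP recommendations. Section 5.8 explains the absence of a board by the use of licensed vaccines in routine care, and allows an independent safety monitor if needed.

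The objection does not remove the mismatch over moderate reactions. It also does not answer the case of a severe entry that the parent records but does not report, because parental notification is the only prompt route the plan describes for it.

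**Conclusion.** The concern holds in limited form. The follow-up described in section 7.4.1 is partly delivered: scheduled staff review inside Days 1–8 is confined to Day 1–2 fever, and everything else depends on the parent reporting it. The notification instruction stops at Grade 3, while section 7.4.1 also names moderate reactions. Sections 7.4.1, 5.1 and 5.6 should be reconciled.

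The exposure is the set of lags in the second table above. They assume that parents make each entry on the day it describes and that contacts occur within the stated windows. They measure time to a scheduled look and say nothing about unscheduled calls, which would shorten them. A Visit 2 later than Day 22 would lengthen the paper lag. The documents give no expected frequency of Grade 3 entries that go unreported, so the number of children affected cannot be estimated. This is a worthwhile, inexpensive improvement to oversight and wording, and does not threaten the trial's results.

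**What to change.** 1. **Sections 5.1 and 6.3.** Set the REDCap memory aid to notify site staff on the day an entry reaches the Grade 3 threshold already used in section 5.6. The existing follow-up in that section would then no longer depend only on the parent's call.
2. **Section 7.4.1.** Reword it to state what is done: which items staff review inside the 8 days, when Grade 2 entries are first read under each diary method, and that severe reactions in paper-only families reach staff promptly only if the parent reports them.

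The cost should be a form setting and a reworded passage, plus a few notices for staff to read. This assumes that the REDCap installation can send such notices. Section 6.3.1 describes automatic range and limit checks but does not mention alerts. The notice would do nothing for paper-only families, and it fires when the entry is made, so a parent who writes on paper and enters later would trigger it late. It also does not address Grade 2, which the rewording must cover. No new clinical threshold or management rule is proposed.
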